## **1. Background and Significance**

### **1.1. *Prevalence, Burden, and Treatment of Traumatic Brain Injury (TBI).***

TBIs are common across both military and civilian populations. In military populations, blast-induced TBI has become a signature casualty of the Iraq and Afghanistan wars [1]. A study of recently deployed personnel estimated that 19% suffered a probable TBI [2]. At this rate, nearly 320,000 military personnel suffered a blast-related brain injury through 2008 [2]. In civilian populations, TBIs from automobile accidents, sports injuries, and other sources rank as one of the leading causes of emergency hospitalizations [3]. In the US, the CDC reports an annual TBI incidence of 1.7 million, with 580,000 TBI-associated deaths in the decade 1997-2007 [3]. Worldwide estimates place the number of annual deaths and hospitalizations associated with TBI at 10 million [4].

For a patient, the burden of TBI extends for months, years, and even a lifetime after the injury. Chronic cognitive deficits have been firmly associated with all severities of TBI. Often, neurocognitive function improves over the first year after injury but plateaus below pre-injury levels [5]. Psychological deficits are also associated with TBI; in a recent study of returning military personnel, 43% of patients who met a criteria for mild TBI suffered from PTSD compared with 16% with other (non-TBI) injuries [2, 6]. TBI can induce depression within months and extending to years after injury [2, 7]. As a result, suicide rates for military personnel with a documented TBI are higher than those without [8, 9]. Sleep disruptions, daytime fatigue, and irritability have all been associated with mild TBI and are sometimes grouped under the label of post-concussive syndrome [10, 11]. Neuromotor impairment is common in severe TBIs; a recent study estimated that one third of severe TBI patients retained neuromotor impairment 2 years following injury [12]. Finally, somatic co-morbidities linked to TBI include pulmonary, cardiovascular, and gastrointestinal dysfunction [2].

### **1.2. *Low-level laser therapy for TBI***

Low-level light therapy (LLLT), also known by low-level laser therapy, is unique among the many therapies tested clinically for TBI. Its mechanism of action is biostimulation by near-infrared (NIR) light, also known as photobiomodulation (PBM). The advantages of LLLT in the brain have been appreciated for over a decade [13]. First, the penetration (~2 cm) of NIR light allows a device placed against the scalp to deliver therapeutic levels of light to the cortex. Second, LLLT is very well tolerated; reports of adverse events in LLLT clinical and case studies are extremely rare [14]. Third, LLLT has a relative short approval pathway because it is regulated as a device that is applied noninvasively through the skin overlying the skull. Because of these unique advantages of LLLT, it is promising as a near-term solution for the immediate

and unmet military and civilian need for TBI therapy.

Over the past decade, multiple studies have demonstrated that LLLT improves recovery in TBI [15-20] and stroke [21-25] models. In parallel to these preclinical efficacy studies, laboratory research has partially deciphered LLLT's mechanisms of action. It is broadly accepted that NIR light absorption within the mitochondrial respiratory chain initiates downstream changes in neuroprotection and vascular function [13].

### 1.3. *Clinical evidence of efficacy and safety supporting a pilot clinical study*

Positive preclinical results motivated a first clinical study of LLLT for stroke. The results of that study, NEST-1, were published in 2007 [26]. This double-blinded placebo controlled study tested the efficacy and safety of LLLT across 120 patients. Light was delivered through a handheld device placed against the shaved scalp. The device was moved to 20 predetermined locations, and held at each location for a duration of 2 minutes. The treated group received LLLT at an average of 16 hours after stroke. Patients were evaluated based on the NIH stroke severity (NIHSS) scale at baseline, +5 d, +30 d, +60 d, and +90 d after stroke. The treatment group in this study showed improved NIHSS over this time-frame ( $p = 0.021$ ). In a follow-up study of 660 patients (NEST-2) [27], a post-hoc analysis of moderate to moderate-severe stroke subpopulation ( $n = 434$  patients) showed a statistically significant NIHSS benefit ( $p = 0.044$ )[40]. A third study (NEST-3) targeting a moderate stroke populations is currently underway.

In addition to providing clinical evidence that transcranial LLLT is effective in treating brain trauma, the NEST-1/2 studies demonstrated a very strong safety profile for the intervention. Detailed safety analyses were performed in both studies of over 700 combined subjects and concluded that LLLT was not associated with any risks within the stroke population of the studies.

Transcranial PBM has not to date been studied as an adjunctive treatment for acute moderate TBI and we would like to conduct a pilot study to assess feasibility. We see this as the first of a series of studies to explore whether LLLT might be useful as a safe and effective treatment for moderate TBI.

## 2. **Specific Aims**

The goal of this research is to assess PBM using LLLT to improve outcomes in subjects with moderate traumatic brain injury (TBI). In this study we use the definition of TBI as described by the DoD: GCS between 9-12 or 13-15 with an abnormal head CT.

The specific aim of this study is to determine the feasibility of PBM with near infrared light emitting diodes (LEDs) using the Photomedex Helmet and to quantify the response to LLLT using magnetic resonance imaging (MRI) and clinical outcome measures. We hypothesize that the Photomedex helmet will successfully deliver LLLT and that we will be able to quantify the response to LLLT through imaging and clinical outcome measures.

**3. Subject Selection**

In this study, we propose to conduct a double-blinded placebo-controlled trial and enroll 90 subjects with moderate TBI to confirm the safety and feasibility to: 1) use the Photomedex Helmet to deliver low-level laser light through the scalp/skull and 2) track the response of delivery through MRI and clinical examinations.

Only patients presenting to the Emergency Department (ED) and/or admitted to the Trauma Service at Massachusetts General Hospital (MGH) will be considered. The following are the inclusion/exclusion criteria for the study.

**Table 1: Selection Criteria**

Inclusion Criteria	I1. At least 18 years old; I2. Injury within 72 hours at the time of consent; I3. Head injury requiring hospital admission;; I4. A Glasgow Coma Scale (GCS) score of 9-12 or 13-15 with abnormal imaging.
Exclusion Criteria	E1. Need for emergency neurosurgical intervention (including placement of intracranial pressure monitoring devices or drainage catheters); E2. Hemodynamic instability as determined by the clinician; E3. History of any of the following: (i) brain tumor; (ii) prior TBI occurring within the past year and requiring hospital admission; (iii) a new diagnosis within the past year of either stroke or epilepsy; (iv) an established diagnosis of any of the following neurodegenerative diseases: Alzheimer’s, Picks, Parkinson’s, Lewy body dementia, Huntington’s, amyotropic lateral sclerosis, spinocerebellar ataxia, vascular dementia, HIZ-associated dementia, dementia due to metabolic causes (Addison, Cushing, hypothyroidism, renal failure, prophyrias, Wilson, mitochondrial diseases, Wernicke-Korsakoff syndrome, and dementia of unknown etiology. E4. Pregnancy (all women of child-bearing age will need to have a negative urine pregnancy test prior to the start of the interventional portion of the study); E5. Electrical implants such as cardiac pacemakers or perfusion pumps; E6. Ferromagnetic implants such as aneurysm clips, surgical clips, prostheses, artificial hearts, valves with steel parts, metal fragments,

**Table 1: Selection Criteria**

	shrapnel, tattoos near the eye, or steel implants, or any other contraindications to MRI. E7. Clinical determination that subject cannot undergo MRI E8. Breastfeeding E9. Unstable cervical fractures E10. Scalp lacerations or surgical wounds severe enough to preclude safe application of device E11. Unreliable to follow up
--	---

#### **4. Recruitment Procedures**

Patients will be approached for enrollment by members of the research team, which include clinical research coordinators and research managers in addition to the PI and other study physicians. Recruitment and enrollment will likely occur in the Emergency Department as it is preferred that the study procedures begin as soon as possible after consent has been obtained. EPIC and other relevant patient databases will be used by qualified research and clinical staff (research coordinators, managers, and study physicians) to electronically identify patients who may be potential candidates for the study. The trauma alert/stat pager may also be used to identify potential subjects by qualified study staff.

We will recruit subjects with head injury according to our inclusion/exclusion criteria. Depending on the type of head injury patients may be admitted as an inpatient or admitted to the ED observation unit.

##### **Admission as Inpatient**

For patients that are admitted as an inpatient, recruitment may require interaction with a surrogate because the patient could have impaired decision-making capacity. All potential subjects are evaluated for the capacity to consent by a physician investigator on the study to determine whether or not surrogate consent is required. When a patient is found to be eligible, a member of the clinical team will first ask the surrogate or patient if they are willing to be approached about a research study. If the surrogate or patient declines, no further attempts will be made to enroll. If the surrogate or patient agrees to speak to someone about the research, a study staff member will approach him or her for discussion of the trial and informed consent, as further outlined in the consent procedures.

##### **Admission to ED Observation Unit**

For patients that are admitted to the ED observation unit, a clinician investigator on the study will evaluate the patient to determine whether or not he or she has impaired decision-making capacity. If the patient has impaired decision-making capacity, a surrogate will be approached. If the patient is not found to have impaired decision-making capacity, they will be asked if they are interested in hearing about our research study. If the surrogate/patient declines, no further attempts will be made to enroll. If the surrogate/patient agrees to speak with someone about the research, a study staff member will approach him or her for discussion of the trial and informed consent as further outlined in the consent procedures.

Patients with a strong likelihood of non-adherence as described in the inclusion and exclusion criteria will not knowingly be enrolled/randomized.

Recruitment will not involve restrictions on sociodemographic factors including gender or ethnic characteristics. Recruitment will be devoid of any procedures which could be construed as coercive. As such, no members of the treating Emergency Medicine teams will be involved in obtaining consent.

## **5. Consent Procedures**

Consent will be obtained by one of the licensed physician investigators listed on the study.

The subjects to be enrolled in this study will have confirmed traumatic brain injury (TBI), requiring hospital admission either to an inpatient floor or to ED Observation. Depending on the severity of the head injury, these subjects may have diminished capacity to provide informed consent at the time of enrollment, and therefore require a surrogate for consent. All patients will be evaluated for the capacity to consent by a physician investigator on the study to determine whether or not surrogate consent is required. If it is found that the patient does have diminished capacity, then surrogate consent will be sought by the physician investigator. Otherwise, the physician investigator will obtain written informed consent from the potential subject.

### **Surrogate Consent**

Initial consent must be sought first from a legal guardian if available, then durable power of attorney if available, then healthcare proxy if available, or if none of these, then from a spouse or other close family member by a physician investigator. However, there may be an opportunity at a follow up time-point, when the subject can be re-consented. During the scheduled follow-up, the subject will be evaluated to determine whether or not he/she has the capacity to consent. If the subject regains the capacity to consent at the follow up they will be consented at this time. If, however, the subject still has diminished capacity but is capable of assent at the time of follow-

up – assent will be obtained. Written assent is not required but any prospective subject who is generally combative or who actively protests about joining the study should not be enrolled, in spite of surrogate consent. Re-consent and/or assent at the time of follow up may be obtained by a non-physician investigator trained on the consent process.

The background of the proposed trial and the benefits and risks of the procedures and trial must be explained to the surrogate. The surrogate must sign the current IRB approved consent form prior to enrollment. This form must be presented to and signed by the surrogate as well as by the consenting investigator physician.

One of the licensed physician investigators listed on the study responsible for consent will approach the surrogate after eligibility has been determined and after the surrogate has agreed to hearing about the research study from someone other than the study staff surgeon, such as a research fellow or study nurse. Assurance that participation in this study is completely voluntary will be given. The investigator physician obtaining consent will explain in detail the protocol of the study, its purpose and potential benefits to society. The surrogate will be informed about minimal risks of routine high magnetic field, non-ionizing RF radiation involved in MR imaging and exposure to the Photomedex Helmet. The surrogate will be informed that if he or she feels uncomfortable with the study, he/she can choose to terminate the study at any time. The surrogate will be informed that their refusal to participate in the study or choosing to terminate it at some point will have no effect on care and treatment received by them now or in future. The surrogate will be informed that their personal information will be protected as per the HIPAA guidelines. Surrogates will typically have less than 12 hours to decide whether or not they wish to consider participation since we are looking to apply the light helmet as soon as possible after injury.

Prior to obtaining informed consent, information will be given in a language and at a level of complexity understandable to the surrogate in both oral and written form by the investigator or assigned designee. The surrogate will not be coerced, persuaded, or unduly influenced to participate or remain in the trial. The surrogate will be given ample time and opportunity to inquire about details of the trial and all questions about the trial should be answered to the satisfaction of the representative.

The subject and his/her surrogate will receive a copy of the signed and dated informed consent form(s).

The surrogate will also provide screening information about the subject for MR compatibility and will give written informed consent prior to the MR imaging study. Informed consent clearly states that the subject and surrogate may choose to terminate the study at any time.

### **Subject Consent**

If the potential subject is admitted to the ED observation unit and found to have full capacity for informed consent, then surrogate consent will not be obtained. Rather, the background of the proposed trial and the benefits and risks of the procedures and trial must be explained to the potential subject. The potential subject must sign the current IRB approved consent form prior to enrollment. This form must be presented to and signed by the potential subject as well as by the consenting investigator physician.

One of the licensed physician investigators listed on the study responsible for consent will approach the potential subject after eligibility has been determined and after the potential subject has agreed to hearing about the research study from someone other than the study staff physician, such as a research fellow or study nurse. Assurance that participation in this study is completely voluntary will be given. The investigator physician obtaining consent will explain in detail the protocol of the study, its purpose and potential benefits to society. The potential subject will be informed about minimal risks of routine high magnetic field, non-ionizing RF radiation involved in MR imaging and exposure to the Photomedex Helmet. The potential subject will be informed that if he or she feels uncomfortable with the study, he/she can choose to terminate the study at any time. The potential subject will be informed that their refusal to participate in the study or choosing to terminate it at some point will have no effect on care and treatment received by them now or in future. The potential subject will be informed that their personal information will be protected as per the HIPAA guidelines. Potential subjects will typically have less than 12 hours to decide whether or not they wish to consider participation since we are looking to apply the light helmet as soon as possible after injury.

Prior to obtaining informed consent, information will be given in a language and at a level of complexity understandable to the potential subject in both oral and written form by the investigator or assigned designee. The potential subject will not be coerced, persuaded, or unduly influenced to participate or remain in the trial. The potential subject will be given ample time and opportunity to inquire about details of the trial and all questions about the trial should be answered to the satisfaction of the representative.

The subject will receive a copy of the signed and dated informed consent form(s).

The subject will also provide screening information about the subject for MR compatibility and will give written informed consent prior to the MR imaging study. Informed consent clearly states that the subject may choose to terminate the study at any time.

## 6. Investigational Device Information

### 6.1. *Helmet Design*

To deliver LLLT acutely to a population of moderate TBI patients, we will acquire two LLLT delivery helmets that are custom manufactured with light-emitting diodes (LEDs) cluster heads arranged uniformly over the inner surface. We will work with Photomedex, Inc. (Montgomeryville, PA) to acquire two LLLT helmet devices (one will serve as a backup device). These helmets will be modified versions of existing prototype devices Figure 1. The Photomedex helmet will sit comfortably on the head and will emit light based energy through multiple LED cluster-heads that are contained inside the custom designed helmet.

Figure 1: Photomedex Helmet Prototype

An array of 360 LED light sources will be located within the helmet. The energy that is generated by the LED sources is photothermal and therefore does not have cumulative mutagenic potential like that of ultraviolet (UV) light. Over the 20 minute procedure, this provides an incident fluence of approximately 43 J/cm^2 (0.036 W/cm^2 x 20 minutes x 60 seconds/minute =

43.2 J/cm^2) to the scalp. Of this energy only approximately 3% or 1.3 J/cm^2 will reach the cortical surface based on known scalp/skull transmission of NIR light in cadavers [28]. Heat generated by the LEDs themselves and by the control electronics will be dissipated by fans located on the exterior of the helmet (see Figure 1). The core temperature of the subject will be monitored during exposure to ensure that there is not an increase of more than 0.5 C during the study procedure. A control unit will be connected to the helmet by a 5 ft cable, and will be used to control the helmet state (on/off/sham).

## 6.2. *Helmet Specifications and Use*

The Photomedex Helmet will be used by experienced study staff members who have undergone training and it will undergo and pass initial electrical safety and quality assurance testing. In addition, the unit will be calibrated once every six months or every ten subjects, whichever happens first, to ensure the intensity does not exceed the specified intensity of 36mW/cm^2 +/- 20%. This is to ensure we are within our power density specifications to maintain data quality and consistency. This testing frequency is based on our confirmation by weekly testing that the LEDs are extremely consistent and reliable in output parameters.

The exposure generated by the Photomedex Helmet is well below the accepted ANSI standard for the safe use of lasers and laser systems (ANSI Z136.1). The accepted maximum permissible exposure (MPE) for skin exposure between 10s-10,000s is 332 mW/cm^2. The Photomedex Helmet will be applied for approximately 1200s (20 minutes) at a power density of 36 mW/cm^2 which is approximately 10 times below the accepted standard. In addition, the fluence of the Photomedex Helmet that will reach the cortex is approximately the same as the reported fluence of the Photothera device used in the NEST-1/2 trials (1.3 J/cm^2 vs. ~1J/cm^2, respectively).

The LED sources will emit at a center wavelength of 810 nm with a bandwidth of 30 nm. The intensity on the scalp will be approximately 36 mW/cm^2 and will be confirmed by a custom-built light monitoring tool to vary by less than 20% across the illumination field.

## 7. **Research Design and Methods**

A member of the study staff familiar with the subject population will evaluate eligibility based on the approved inclusion/exclusion criteria, using patient charts. If a subject is eligible a physician on the study staff will approach the subject and/or surrogate for informed consent (please see consent procedures for more details). Demographic and clinical data will be collected during the acute hospitalization in accordance with the common data elements proposed by the TBI Common Data Element Project [29]. A drop point for deterioration for

withdrawing a subject will be a change in the GCS of greater than 2 from the previous exam.

After informed consent has been obtained, the subject will be randomized. All subjects will undergo either treatment or sham (placebo) procedures. In the sham procedure, the helmet will be placed on the patient but the LEDs will not be activated. The randomization will be set up so subjects are assigned sequentially into one of 9 groups with 10 subjects in each group. Within each group, the subject will be assigned randomly to either treatment or sham with an allocation ratio of 1:1. Once the first 10 subjects have been enrolled and have finished treatment (or sham) a DSMB (see detailed description under data safety and monitoring) will go over all of the safety data presented and make a recommendation on the continuation of the study. Subsequent DSMB meetings will take place once per year

If the subject is admitted to the ICU, he/she, will be treated according to the ICU standard of care procedures.

- Standard of care procedures include:
- Monitoring of O2/CO2 levels;
  - Avoiding hypotension;
  - Maintaining temperature within normative range;
  - Adjusting cervical collar placement if necessary;
  - Repeat CT scan if necessary;
  - Bed placement at > 30 degrees while in the ICU
  - Sedation and analgesia using recommended agents

If the subject is admitted to the ED Observation Unit, he/she will be treated according to the ED standard of care procedures.

The application of the Photomedex helmet will be in addition to but will not change the standard of care.

The following table summarizes the timing and specific assessments to be conducted in this study:

ASSESSMENTS	PRE-PROCEDURE	PROCEDURE	FOLLOW UP
Eligibility Assessment	X		
Informed Consent Form a	X		
Demographics, including date of birth, gender, and race and ethnicity	X		
Medical History	X		
Pregnancy Test b	X		X
Investigational LLLT using the Photomedex		X	

Helmet			
Neuroimaging using Magnetic Resonance		X	X
Clinical Outcomes Assessment		X	X
AE, SAE, UADE Assessment		X	X

a If the subject regains capacity they will be re-consented at the time of follow up.

b Exclusion criteria (E4.) specific for female subjects of childbearing age.

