### 7.1. *LLLT Photomedex Helmet Device Application*

In order to maintain blinding, a study staff member not associated with analysis of the study will create a randomization code and assign treatment via an envelopment randomization system. The study staff member in charge of applying the Photomedex helmet will open each randomization envelop and once the clinician deems it is acceptable, subjects will undergo approximately 20 minutes of exposure to the Photomedex helmet within 72 hours after injury. If the subject is assigned to the sham group the LEDs will not be activated. Because the helmet uses NIR light that is invisible to the human eye, clinical staff within the room will not be able to detect whether the LEDs are activated.

The Photomedex helmet will be used up to 3 times for each subject. The first application will be as soon as possible after injury, within 72 hours. Follow up applications of the Photomedex helmet will be applied for up to 2 additional time points no sooner than 12 hours after the previous helmet application. If the subject is discharged from the hospital prior to the second helmet application, a follow up helmet application will be scheduled. If the subject wishes to have the option to complete in-person visits at his/her place of residence or another location, they will indicate this by signing the LLLT Out of Hospital Follow Up Consent Form at the time they enroll in the study.

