### **12.1. *Data and Safety Monitoring***

The PI will be responsible for overseeing all aspects of the study including: ensuring that the study is conducted according to the IRB-approved protocol, performing monitoring and confirming compliance of the study, and protecting the rights, safety and welfare of the subjects. Should the PI at any point feel that the health and well being of the subject is compromised the study procedures will be immediately suspended.

Data will be collected by the appropriate study staff, such as research fellows from the Department of Trauma, Emergency Surgery and Surgical Critical Care. Case report forms will be kept securely in the electronic Partners Redcap Database. In addition, electronic data will be stored on a Password Protected computer system and backed up onto a secure server location. Only the PI and research team will have access to the database, and identifying information will not be released. The data will be reviewed regularly by the designated study staff and the PI will regularly review the data and findings with the study staff during a regularly held research meeting. Throughout the duration of the study, the PI will perform ongoing evaluation of subject safety data in order to identify AEs and trends as soon as possible. The PI will be responsible for determining whether the research should be altered or stopped. In addition, de identified image MRI image data will be shared with external collaborators in order to perform quantitative image analysis through a customized computational algorithm. The data will have all identifiers removed and will be transferred to the collaborator by a study staff member.

A designated study staff member will be responsible for gathering post-procedure follow-up data on the subject. The subjects will be followed until discharge. We will also follow-up with the patient 3 and 6 months after injury. A follow up phone call will be completed at 12 months.

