In order to review the data in an unblinded fashion, we will establish a DSMB of experienced specialists from Trauma, Neurology, Radiology, Rehabilitation at MGH and Spaulding, and the Wellman Center at MGH who are not conflicted or study staff members to review the safety data. The DSMB will review the data collected after the first 10 subjects have been enrolled. The DSMB will make a recommendation as to whether or not the study should continue. If the DSMB recommends continuation of the study, subsequent DSMB review of data once per year.

Additionally, [name] MD, a neurologist at MGH and member of the DSMB will serve as an independent research monitor for the study. He will review the research protocol with the

investigators, review the monitoring plan, and review study data. If the research monitor is concerned for the safety and well-being of the subjects he/she will have the authority to stop the research protocol in progress, remove individual human subjects from a research protocol, and take whatever steps are necessary to protect the safety and well-being of human subjects until the IRB can assess the monitor's assessment. The research monitor will review all unanticipated problems involving risk to subjects or others, device-related serious adverse events and all subject deaths associated with the protocol. At a minimum, the research monitor must comment on the outcomes of the event or problem and in case of a device-related serious adverse event or death, comment on the relationship to participation in the study. The research monitor must also indicate whether he/she concurs with the details of the report provided by the principal investigator. The research monitor will provide an unbiased written report Reports for events determined by either the investigator or research monitor to be possibly or definitely related to participation and reports of events resulting in death will be promptly forwarded to the USAMRMC ORP HRPO.

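### The GCS deterioration rule withdraws the subject rather than stopping the helmet, and no visible text keeps that subject in follow-up

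*Protocol*

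**What the plan says.** Protocol Section 7 (Research Design and Methods) states the rule in one sentence. It opens "A drop point for deterioration for" and goes on "withdrawing a subject will be a change in the GCS of greater than 2 from the previous exam". The rule acts on the subject; the helmet is not mentioned. The preceding sentence is about data gathered during the acute admission. The following one, which opens a new paragraph, is "After informed consent has been obtained, the subject will be randomized".

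Treatment is repeated. After the first application, Section 7.1 allows "up to 2 additional time points no sooner than 12 hours after the previous helmet application".

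Two clauses in Section 12.1 can also interrupt participation. If the principal investigator thinks a subject's wellbeing is compromised, "the study procedures will be immediately suspended". The research monitor may "remove individual human subjects from a research protocol". Neither clause says what happens to follow-up.

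Follow-up is laid down for subjects in general. The assessment table in Section 7 has a row for "AE, SAE, UADE Assessment" at the procedure and at follow-up. Section 7.3 lists the visits, calls and scans, and Section 12.1 adds "We will also follow-up with the patient 3 and 6 months after injury". None of these places mentions a withdrawn subject. Section 10 (Adverse Events) sets no follow-up period. The SAP puts into the DTI analysis every patient who had at least one MRI.

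**The concern.** Stopping a study treatment and ending a subject's participation are different decisions. Deterioration is a good reason for the first. It is a poor reason for the second, because it selects for missing data exactly those subjects whose course matters most for safety.

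The primary endpoint in the synopsis counts subjects who complete the study without device-related adverse events. A withdrawn subject is visible as a non-completer, but judging whether the event was device-related, and how it ended, needs the later course. Section 10 treats death only as the outcome of the adverse event that led to it, and Section 12.1 requires the research monitor to comment on outcomes for the events under review. Both depend on follow-up that the rule, read literally, may end.

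For imaging, the baseline MRI comes after the first helmet application (Section 7.2). Withdrawal between the two is therefore a post-treatment exclusion from the DTI set, triggered by worsening. For later scans, the SAP's mixed model is valid only if missing time points are missing at random given what is modelled, and GCS is not among its stated terms.

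**Working it through.** **1. When does the rule apply?** The text allows two readings.
- *Before randomisation only.* The sentence stands just ahead of the randomisation sentence. On this reading neither arm loses any data.
- *After randomisation.* Withdrawing a subject presupposes someone already in the study, comparison with the previous exam implies serial exams, and the sentence before concerns the acute admission. Up to 3 applications at least 12 hours apart leave time for the rule to be met. This is the more natural reading.

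**2. What happens next?** No visible text says. The schedules in Sections 7, 7.2, 7.3 and 12.1 neither include nor exclude withdrawn subjects.

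**3. The plan's sample size.** Inputs from Section 9: effect 25%, CV of FA 40%. With two-sided 5% and 80% power (the SAP gives 0.05; sidedness and power are my assumptions), the rule of thumb is

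n per arm = 16 × CV² / effect² = 16 × 0.40² / 0.25² = 40.96, rounded up to 41; total 2 × 41 = 82.

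This reproduces the plan's figure. With up to 90 enrolled, the margin is 90 − 82 = 8. Calculated power is 84.2% at 45 per arm and 80.8% at 41 per arm.

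**4. Loss per subject, if the rule operates after randomisation and ends follow-up.** Inputs:
- Contacts (Section 7.3): day-7 call, visits at 14–21 days, 3 months and 6 months, 12-month call = 5.
- MRIs (Sections 7.2 and 7.3): baseline, 14–21 days, 3 months = 3.
- DTI values per parameter (SAP): 18 tracts × 3 time points = 54.

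| Withdrawn in hospital | Contacts lost | MRIs lost | DTI values lost per parameter | In DTI set? |
|---|---|---|---|---|
| Before first MRI | 5 of 5 | 3 of 3 | 54 of 54 | No |
| After first MRI | 5 of 5 | 2 of 3 | 18 × 2 = 36 of 54 | Yes |

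The window for the first row is roughly the 24–48 hours that Section 7.2 expects between enrolment and MRI, longer if the scan is deferred. The MRI columns are upper bounds: Sections 7.2 and 11.1 already defer scans in subjects who cannot be scanned or moved safely.

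**5. Loss across the trial.** The documents give no trigger rate. Assume 1 to 5 of 90 subjects.
- Contacts: 90 × 5 = 450 planned; lost 1 × 5 = 5 to 5 × 5 = 25, or 1.1% to 5.6%.
- Scans: 90 × 3 = 270 planned; lost 1 × 2 = 2 to 5 × 3 = 15, or 0.7% to 5.6%.
- Subjects: even 5 unscanned leave 90 − 5 = 85, above 82. It would take 9 (90 − 9 = 81) for this rule alone to go below 82.

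On the pre-randomisation reading every loss is 0.

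**The case against.** The strongest reply is that the harm needs two conditions the text does not establish: that the rule operates after randomisation, and that withdrawal ends all data collection. Follow-up to discharge is stated twice (Sections 7.2 and 12.1), and the later contacts carry no exception for subjects who met the criterion. The consent pages are not in the copy reviewed, so wording there on data after withdrawal is unknown and cannot be counted as absent. All this makes the loss conditional. It does not remove the gap, because a general schedule does not say that it overrides a specific withdrawal rule.

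A reader might infer that the rule hides the safety signal. The documents do not support that. Worsening of the underlying condition is reportable (Section 10), the principal investigator reviews safety data continuously, the DSMB sees data unblinded, and the research monitor reviews device-related serious events, unanticipated problems and deaths associated with the protocol (Section 12.1). What can be lost is the later course, not the event.

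A reader might also infer that the DTI comparison is biased or underpowered. That is not shown either. The rule is the same in both arms, Section 7.1 says that clinical staff in the room cannot tell active from sham, and some deteriorating subjects would go unscanned whatever the rule said.

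Finally, the temperature rule in Section 11.2, which removes the helmet and does not mention withdrawal, is a useful wording model. It is no evidence that follow-up continues, since it is silent on that too.

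**Conclusion.** The point stands as a conditional weakness of minor to moderate severity. The rule names withdrawal of the subject as the consequence of deterioration, and no visible text keeps that subject in follow-up. Applied literally after randomisation, it can end adverse-event and clinical follow-up, and possibly MRI, in subjects selected for getting worse. A subject withdrawn before the first MRI also leaves the DTI set.

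The size rests on assumptions: post-randomisation use, withdrawal meaning the end of data collection, and an assumed 1 to 5 triggers. Under them, losses are at most 5.6% of contacts or scans. The 8-subject margin is unlikely to be used up by this rule alone. Any DTI bias is probably small, and its direction cannot be told from the documents. The case for change is the missing course of a few important subjects, not power.

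**What to change.** Replace the sentence in Section 7 with:

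> A GCS decrease of more than 2 from the previous exam stops further helmet applications. The subject stays in the randomised arm, and scheduled AE and clinical follow-up, and MRI where clinically safe, continue unless the subject or surrogate withdraws consent. If a self-consented subject loses capacity, surrogate permission is sought for further research procedures.

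Specifying a decrease also removes the literal possibility that an improvement triggers the rule. The capacity clause is needed because Section 5 has no surrogate for a subject in ED observation who consents with full capacity, and provides for regaining capacity but not for losing it. The threshold itself is for the clinicians.

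In the safety report, give GCS-triggered stops by arm, with timing relative to the first helmet application.

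The cost is one reworded rule and one reporting line per arm; the visits and calls are already scheduled. The downside is following a few sicker subjects, some of whom will still go unscanned, and a surrogate contact for some. The SAP is written in the past tense. If conduct is complete, rewording cannot recover data, and the by-arm report is the part that remains useful.
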